7.2 Study Overview

7.2.1 Description

RESOLUTION is a multicentre, randomized, double-blind (patients, Investigators and blinded study staff), placebo-controlled Phase II study of LAU-7b for the treatment of COVID-19 disease in patients at a higher risk than the general COVID-19 disease population to develop complications while hospitalized.

To be eligible for the study, patients must be symptomatic of COVID-19, confirmed by PCR (or alternates but excluding rapid antigen tests)) to have a SARS-CoV-2 infection, be aged 18 years and above, and meet all other study inclusion and none of the exclusion criteria at screening. There is no time limit between the onset of symptoms or the confirmation of SARS-CoV-2 infection and screening.

Eligible patients will be randomized 1:1, at each clinical site, to either LAU-7b (active) group or placebo (control) group. After randomization, patients will enter the treatment phase of the study. There will be no active control treatment but patients will undergo the COVID-19 disease SOC at their institution.

Since the study randomizes only confirmed cases of SARS-CoV-2 infection, the screen failure rate is very low. It is estimated that based on sample size calculation using the effect size observed in the pilot portion of the study for the revised Primary Efficacy Endpoint in the subset of patients with Health Status score 3 or 4 at baseline, up to a total of approximately 264 patients with a Health Status score 3 or 4 at baseline will be recruited in the expansion. Patients will be enrolled at approximately 25-30 centers in the United States of America and in Canada. The study treatment (LAU-7b or matching placebo) will be administered once a day in the fed state (with the main meal of the day if possible) for up to 14 days on treatment.

Patients will be evaluated at pre-specified times during and after the study treatment period, for efficacy, safety, as well as for Quality of Life.

This design is appropriate for this phase of development (confirmatory Phase 3 portion) and will ensure that the highest quality of data is collected with minimal bias and the patient's safety and wellbeing are preserved. A Data and Safety Monitoring Board (DSMB) is monitoring this study.

The overall study structure for Health Status 3+4 patients in the Phase 2 pilot and the Phase 3 extension is presented below in Figure 2.

[figure not shown]

Figure 2: Overall structure of the study

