8.3 Study Drug Discontinuation and Withdrawal of Patients

Patients should discontinue permanently the study drug in the event of any of the following (Since a low LAU-7b dose is used in this study, no dose reductions are planned):

- 1. If a patient is escalated to invasive mechanical ventilation preventing the administration of the study medication intact;
- 2. Occurrence of a SAE deemed related to the study drug that is a life-threatening adverse reaction or one resulting in prolonged non-COVID-19 disease-related hospitalization;

LAU-7b for the treatment of COVID-19 disease in Adults

² When a factor that may potentially affect renal function by hemodynamic mechanisms is known or suspected on admission (Ex: dehydration), it is recommended to rule out a possible renal impairment by addressing the issue whenever possible (Ex: rehydration) and reassessing CrCL prior to signing the ICF.

- 3. If the patient, Investigator, or Laurent determines that it is not in the best interest of the patient to continue treatment;
- 4. If a patient is serially and persistently noncompliant with study procedures and/or assessments, the investigator or the sponsor may withdraw the patient from further treatment;
- 5. A patient's treatment is unblinded by the Investigator;
- 6. If a female patient has a confirmed pregnancy (with the exception of a pregnancy resulting from *in-vitro* fertilization), this should be immediately reported to the Medical Monitor and Laurent Pharmaceuticals (within 24 hours awareness) and the patient shall discontinue the study drug. Pregnancy, whether in a patient or in a partner of a patient should be followed up until conclusion, with an assessment of child health at birth:
- 7. Considering the safety observed so far in the study, patients showing possible kidney impairment as depicted by either:
 - a. An increase from screening in serum creatinine of 0.5 mg/dL or 2x the screening value if the serum creatinine was within normal range at screening and the calculated CrCL was \geq 30 ml/min;
 - b. An increase of serum creatinine $\geq 2x$ the screening value if the screening value was above the normal range and the calculated CrCL was ≥ 30 ml/min.
- 8. Notwithstanding that the study so far confirms the lack of a particular drug-related liver toxicity, patients showing possible liver impairment as assessed with the liver safety algorithm based on the Drug Induced Liver Injury (DILI) algorithm, described in Section 11.4

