11.2 Clinical Laboratory Assessments

Blood and urine samples will be collected according to the Schedule of Events (page 11) and analyzed locally at the clinical site's laboratory as per their SOC. Laboratory test results that are abnormal and considered clinically significant must be reported as AEs (as per Section 11.1.1). Screening laboratory results must be available and reviewed by the Investigator before randomization. The typical safety laboratory test panels are shown in Table 2 below (it is acceptable that SOC varies between clinical sites regarding some tests, but testing must include at the minimum tests evaluating the hematologic status, the kidney and the liver functions. The tests marked by a (+) are suggested:

Table 2: Laboratory Tests Panels

Serum Chemistry	Hematology	Urinalysis*	
Albumin+	Hematocrit+	Nitrite	
Creatinine+	Hemoglobin+	Urobilinogen+	
Total protein	Red blood cells+	Protein+	

Potassium Mean corpuscular hemoglobin pH+
Sodium Mean corpuscular hemoglobin Blood+

Calcium Mean corpuscular volume Leucocyte esterase
Bicarbonate Reticulocytes Specific gravity

PhosphatePlatelet count+KetonesAlkaline phosphatase+Leucocytes+Bilirubin+ALT+Differential (absolute and %)Glucose+AST+EosinophilsAppearance

GGT Basophils
Total bilirubin+ Neutrophils+
Blood urea nitrogen+ Lymphocytes+
Glucose Monocytes

For the purpose of this study conduct, the laboratory tests performed in the local laboratory are the primary tests. Normal ranges and accreditations should be current and filed in the Investigator Site File and in the study's Trial Master File.

In addition, according to the Schedule of Events, pregnancy tests (β -human chorionic gonadotropin) for females of childbearing potential: Urine (or serum) samples will be obtained as specified in the Schedule of Events, page 11 and tested. The urine (or serum) pregnancy test pre-randomization must be negative before the first dose of study drug. Finally, clinical laboratory evaluations may be performed at other times if judged to be clinically appropriate by the Investigator.

Reporting requirements for laboratory tests performed to monitor a SAE, in addition to the protocol-requested safety laboratory tests: Patients experiencing a worsening of their condition (generally a life-threatening situation declared as a SAE) are subject to receiving numerous con-meds, spontaneous treatment adjustments, along with frequent safety laboratory testing.

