11.4 Liver Safety Algorithm for the Management of Hepatic Impairment

The following instructions are to be followed if liver function markers and clinical presentation suggest the onset of hepatic impairment on study. The hepatic safety of all randomized patients will be assessed through the use of the following algorithm based on FDA DILI management guidelines:

- If ALT or AST rises > 5x the Upper Limit of Normal (ULN): LAU-7b treatment is discontinued and patient is closely monitored until recovery;
- If subjects with abnormal baseline liver indices develop elevations of AST or ALT >2x the baseline values or total bilirubin (TBL) >1.5x the baseline values during the study, repeat testing should be performed within 48 -72 hours. If there are persistent elevations (ALT or AST >2x the baseline values or TBL >1.5x the baseline values) upon repeat testing, LAU-7b should be discontinued unless LAU-7b is clearly not the cause of the elevation;
- If baseline measurements were <2x ULN, discontinue LAU-7b if ALT or AST increases to > 4x the baseline values;
- If baseline values are ≥2x ULN but <5x ULN, discontinue LAU-7b if ALT or AST increases to > 2x the baseline values;
- Discontinue LAU-7b if ALT or AST increase >2x the baseline values *AND* the increase is accompanied by a concomitant increase in TBL >1.5x the baseline value *OR* the International Normalized Ratio (INR) concomitantly increases by >0.2
- Discontinue LAU-7b treatment if alkaline phosphatase increases to > 2x the baseline value.
- Discontinue LAU-7b in any subject with multiple signs or symptoms suggestive of liver injury such as fatigue, nausea, vomiting, right upper quadrant pain or tenderness, fever, rash, and/or eosinophilia (> 5%).

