12 STATISTICAL ANALYSIS

A statistical analysis plan (SAP) will provide details of the methods of analysis to address all study objectives. The SAP may be amended during the course of the study, but will be finalized before the cutoff date for any analysis, interim or final.

Data summaries by treatment group will be presented. For categorical data such as the 7-point Ordinal Scale, data will be tabulated in frequency tables to display the number and proportion of patients for each category by treatment group. For continuous variables, data will be summarized with the number of patients, mean, standard deviation, median, and minimum and maximum values by treatment group. Baseline assessments for each outcome variable will be defined as the screening measurement unless a repeat value was obtained, see restrictions in Section 9.2.1.1, before the first dose of study drug. Statistical significance will be set at the 5% level (one-sided) for the pilot portion and at the 5% level (two-sided) for the extension. Consideration

will be given for adjusting for pre-specified prognostic baseline factors such as age, the ordinal scale health status at baseline and comorbidities, where applicable.

Diligent efforts will be made to prevent missing data in the study. For example, patients who discontinue the study treatment early should still be followed for all regularly scheduled visits for safety and relevant efficacy assessments, until the Day 60 follow-up. A clear distinction should be made between treatment discontinuation and study withdrawal. Efficacy assessments occurring after treatment discontinuation should not be included in the per-protocol analysis.

Database lock and statistical analyses will be performed for the pilot portion and the extension, separately.

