12.8 Safety Analyses

The safety analyses will be performed at least five times, 1- when a minimum of one third of the initially enrolled patients have completed their LAU-7b (or placebo) treatment period and corresponding safety information is available, 2- when at least two thirds of the initially enrolled patients have completed their LAU-7b (or placebo) treatment period, 3- at the time of final analysis subsequent to the planned database lock on 15Sep2021 for the pilot part of the study, 4- when at least half of the expansion's enrolled patients have completed their LAU-7b (or placebo) treatment period, and 5- at the time of final analysis (after completion of the expanded enrolment and database lock). Safety analyses will be performed on the safety population (those patients who receive at least one dose of study drug). Blinded safety data will be assessed by the DSMB at regular meetings. The DSMB may request unblinding of patients for safety concerns in addition to receiving the unblinded interim analyses results. Like it was the case for the pilot portion of the study, the study expansion will be double blinded to the Investigators, patients and sponsor's staff until the revised end of the study, unless circumstances require unblinding.

Safety and tolerability will be assessed by the following:

- Adverse events described and categorized according to the MedDRA, version 16 or more recent.
- Clinically relevant changes from baseline in vital signs
- Clinically relevant changes from baseline in directed physical examinations
- Clinically relevant changes from baseline in safety laboratory assessments (hematology with differential count, biochemistry, and urinalysis).

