12.8.2 Clinical Laboratory Assessments

Safety laboratory variables (e.g., hematology, biochemistry, and urinalysis results) will be presented in SI units, if available, at each time point using descriptive statistics (mean, standard deviation, median, minimum, and maximum).

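### Section 12.8.2 plans no by-arm count of patients meeting the protocol's own liver and kidney laboratory limits, and the adverse event tables fill that gap only partly

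*Protocol*

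**What the plan says.** - **Laboratory summary (Protocol 12.8.2).** Variables "will be presented in SI units, if available", and are summarized "at each time point using descriptive statistics (mean, standard deviation, median, minimum, and maximum". Section 12 supplies the arm split: "Data summaries by treatment group will be presented". Section 12.8.2 mentions no change from baseline, shift table, multiple of ULN or baseline, worst value, or count beyond a limit.
- **Stated intention (12.8).** Safety is to be assessed by, among other things, "Clinically relevant changes from baseline in safety laboratory assessments (hematology with differential count, biochemistry, and urinalysis". Clinical relevance is not defined and no table is attached to it.
- **Source of the values (11.2, 7.2.1).** Samples are "analyzed locally at the clinical site's laboratory as per their SOC". "Patients will be enrolled at approximately 25-30 centers in the United States of America and in Canada".
- **Limits that stop study drug (11.4, 8.3 item 7).** The liver rules start with "If ALT or AST rises > 5x the Upper Limit of Normal (ULN". They go on to multiples of baseline for ALT, AST, total bilirubin and alkaline phosphatase. The kidney rules are a creatinine rise of 0.5 mg/dL or a doubling from screening, and, for patients already above normal, "An increase of serum creatinine" to at least twice the screening value.
- **Sampling (9.2.3 to 9.2.6, 11.2).** After screening, tests are done on Days 5, 8 and 12 while the patient is in hospital, and at discharge or Day 14 unless one was done within 2 days. Later contacts include none. Results after intubation need not be entered in the eCRF.
- **Vital signs (12.8.3).** These receive change from baseline by arm and the number and percentage of patients meeting abnormal criteria.

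**The concern.** The protocol treats certain laboratory changes as serious enough to stop study drug, and writes those limits on the ULN scale, the baseline scale or, for creatinine, a change in mg/dL. Its laboratory analysis uses raw SI units by visit day. A raw value of ALT pooled across 25-30 local laboratories does not show where each patient stands against the local ULN or his or her own baseline. Liver and kidney signals usually appear in a few individuals and barely move a mean.

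The set of patients behind each by-day summary also changes after randomization. Days 5, 8 and 12 cover only those still in hospital, and intubated patients can drop out of the recorded data. If the arms differ in speed of discharge or rate of intubation, the by-day columns no longer compare the randomized groups.

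At stake is the strength of a hepatic and renal safety statement. Two arms with different numbers of patients beyond a limit could produce similar planned tables.

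**Working it through.** The plan gives no figure to reproduce here. The check sets the sections side by side and then uses labelled assumptions to show scale.

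**1. Planned output against the limits**

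| Limit | Scale | Shown by 12.8.2? |
|---|---|---|
| ALT or AST > 5x ULN (11.4) | local ULN | No; raw units only |
| ALT or AST > 4x or > 2x baseline (11.4) | patient's baseline | No; no change from baseline |
| Total bilirubin > 1.5x, alkaline phosphatase > 2x baseline (11.4) | patient's baseline | No |
| Creatinine +0.5 mg/dL or 2x screening (8.3 item 7) | patient's screening value | No |

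The planned maximum shows that at least one extreme value exists at a visit. It does not show how many patients had one, or at what multiple.

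**2. Effect of local ranges (assumption: local ALT ULN between 35 and 55 U/L)**

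Multiple = value / ULN. For 200 U/L: 200/35 = 5.7 and 200/55 = 3.6. The 5x limit falls at 5 x 35 = 175 U/L at one site and 5 x 55 = 275 U/L at the other. Any raw value between 175 and 275 U/L could lie on either side of the limit, depending on the site.

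**3. Dilution in the mean (assumptions: all 132 patients per arm sampled; unaffected patients mean 40, SD 25 U/L; affected patients at 240 U/L)**

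With k affected of n, let p = k/n. Mean shift = p x (240 - 40). SD = sqrt[(1 - p) x 25² + p(1 - p) x 200²].

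- k = 3: p = 2.3%, shift 4.5 U/L, SD 38.7.
- k = 6: p = 4.5%, shift 9.1 U/L, SD 48.3.

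The same data as counts, with two-sided Fisher p = 2 x C(132,k)/C(264,k) for k against 0:

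- 6/132 against 0/132: p = 0.029.
- 3/132 against 0/132: p = 2 x (132 x 131 x 130)/(264 x 263 x 262) = 0.25.

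The second count is not statistically distinguishable from chance, but the reader can see it. A mean shift of 4.5 U/L against an SD near 39 is easily overlooked. The p-values only show scale; no formal test is proposed.

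**4. Do the adverse event tables supply the count?**

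Section 11.1.1 makes a laboratory abnormality an adverse event if it leads to discontinuation, treatment, further work-up or significant symptoms. Section 12.8.1 tabulates events leading to discontinuation and events by maximal severity. But 11.1.1 also lists two categories not reported in the eCRF. One is clinically significant laboratory variation, with transaminitis among the examples, that could result from COVID-related acute care. The reason given refers to ventilated patients; the laboratory item itself is not limited to them. Section 11.2 says clinically significant abnormal results must be reported as adverse events. These two instructions conflict for a patient whose ALT rise might come from COVID care, so the adverse event tables cannot be relied on for the count.

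**The case against.** The strongest reply has four parts.

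- **The full plan is elsewhere.** Section 12 defers detail to the SAP, and the SAP addendum sends readers to the main SAP of 29SEP2023, which was not available here. This stands. A reader might infer that laboratory limits are never compared by arm; the documents do not support that, because the main SAP may contain such tables.
- **There is an indirect by-arm route.** Meeting a limit generally stops study drug, the reason goes on the CRF (8.3), and resulting adverse events are tabulated by arm. Section 12.8 also names laboratory changes from baseline. So it would be wrong to say that raw values are the only laboratory safety information planned. The route remains partial, because of the exclusion in 11.1.1 and its dependence on investigator attribution.
- **Not all laboratory data come from patients still in hospital.** The discharge/Day 14 sample gives most early-discharged patients an end-of-stay value. This stands and partly offsets the changing sample. Nor can one infer that each later day holds a steadily sicker group: patients may leave the recorded data by intubation as well as by discharge. The documents give no length of stay, so the size of this effect cannot be stated.
- **Not every limit can be counted.** INR is part of an 11.4 criterion but is not in Table 2. One criterion rests on symptoms, and another on repeat testing with a causality exemption. Tests done to monitor an SAE are not entered in the eCRF. This stands and restricts the remedy to recorded, computable limits.

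**Conclusion.** The point holds in a limited form. In the documents available, Section 12.8.2 reports laboratory values from local laboratories only as SI-unit descriptive statistics by time point. It plans no by-arm count against the limits in 11.4 and 8.3 item 7. That falls short of the intention stated in 12.8 and of the treatment given to vital signs in 12.8.3. Adverse event and discontinuation tables cover part of the gap.

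The size cannot be fixed from the documents. The ULN range of 35-55 U/L and the ALT values in the dilution example are assumptions that show the mechanism; the conclusion does not depend on them. No efficacy result is touched. What is affected is how firmly the report can state that the arms were alike in liver and kidney safety. The conclusion rests on the main SAP not already containing these tables.

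**What to change.** Add to Section 12.8.2, or to a further SAP addendum, by arm in the safety population:

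1. Each patient's worst recorded post-baseline value, including discharge/Day 14, for ALT, AST, total bilirubin, alkaline phosphatase and creatinine, as a multiple of the local ULN and of baseline.
2. Baseline-to-worst shift tables.
3. Number and percentage meeting each 11.4 and 8.3 item 7 limit that can be computed from recorded laboratory values.
4. Number of patients sampled at each time point, with the by-day summaries kept as supportive.

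State the limits of the count: SAE-monitoring and post-intubation tests are not in the eCRF, INR is not in Table 2, and symptom-based or causality-dependent criteria are not counted.

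Reconcile two sets of text first. In 11.4, patients with abnormal baseline liver values below 2x ULN fall under both a 2x-baseline rule (persistent on repeat) and a 4x-baseline rule. The exclusion in 11.1.1 also needs to be squared with the reporting requirement in 11.2.

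**Cost.** Some programming, plus entry of local normal ranges. Section 11.2 has these filed in the site and trial master files, but nothing says they are in the database. No new samples are needed. Because results were first released on 14MAR2024, label the tables post hoc. If the main SAP already contains them, citing it closes the point.

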12.8.3 Vital Signs

Vital signs (blood pressure, temperature, heart rate, oxygen saturation and respiration rate) will be presented at each time point using descriptive statistics (mean, standard deviation, median, minimum, and maximum). Change from baseline values for each variable will also be presented by treatment group.

The number and percentage of patients that meet the abnormal criteria for with shift changes from baseline of the vital signs during the TEAE period will be presented by treatment group. The specific changes of interest are:

- Diastolic Blood Pressure ≤45 mmHg and decrease from baseline ≥10 mmHg, Diastolic Blood Pressure ≥110 mmHg and increase from baseline ≥10 mmHg;
- Systolic Blood Pressure ≥160 mmHg and increase from baseline ≥20 mmHg, Diastolic Blood Pressure ≤45 mmHg and decrease from baseline ≥10 mmHg;
- Temperature ≤35°C and ≥38°C
- Heart rate ≤50 bpm and decrease from baseline ≥20 bpm, heart rate ≥120 bpm and increase from baseline ≥20 bpm;
- Oxygen saturation values and respiratory rate determined by the Investigator to be clinically abnormal (and reported as an AE). More specifically, the incidence of oxygen saturation being 92% or lower when measured in patient stabilized on room air, will be presented by treatment group.

No statistical analyses of vital signs are planned.

